Lactogenesis stage II signals the change from production of small quantities of colostrum to copious amounts of breast milk. This stage occurs following delivery due to a dramatic decrease in progesterone and maintenance of prolactin levels (Kuhn, 1983). Initiation of lactogenesis stage II is experienced by the woman in what is referred to as (a) "milk coming in" or feelings of notable fullness in her breasts (Perez-Escamilla & Chapman, 2000) and (b) increases in milk volume to over 100ml/d (Neville et al., 2001). Maternal perception of a sudden feeling of fullness in the breast has been a traditional method of determining the timing of lactogenesis stage II and is correlated with actual timing of this stage (Perez-Escamilla & Chapman, 2000).

Delayed Lactogenesis Stage II

Lactogenesis stage II usually occurs approximately 30-40 hours following the birth of full-term infants (Hurst, 2007), but delay has been known to occur in 22 to 31% of women who deliver at term (Dewey, Nommsen-Rivers, Heinig, & Cohen, 2003). Delayed or impaired lactogenesis stage II has been found in up to 82% of women who deliver prematurely (Henderson, Hartman, Newnham, & Simmer, 2009; Cregan et al., 2001). Delayed progression to stage II among women who deliver full-term has been associated with delayed initiation of breastfeeding, gestational diabetes, obesity, cesarean section, prolonged second stage of labor, primiparity, administration of pain medications during labor, breast implantation and reduction mammoplasty (Chen, Nommsen-Rivers, Dewey, & Lonnerdal, 1998; Hildebrandt, 1999; Morton, 1994; Neifert, et al., 1990; Neubauer et al., 1993).

Delayed lactogenesis stage II has both immediate and longer-term negative consequences. If such delays result in an inadequate amount of breast milk for infant consumption, breast milk feedings are replaced with commercially prepared formula, or feedings are withheld until breast milk is available. Both options may be potentially detrimental to the VLBW infant. Since both intestinal and gastric hormone secretion and motility are dependent on enteral feedings, a delay in feeding can potentially decrease future feeding tolerance (Berseth, 1990). Provision of even small amounts of formula is associated with abnormal changes in the microflora of the

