In a survey of 80 obstetrical nurses from 3 large hospitals in Florida, over 30% stated that a major barrier to assisting mothers of VLBW infants to begin timely breast milk expression following delivery was a lack of time and lack of personnel.

Primary purpose of this pilot study is to determine the feasibility and potential effect of a prenatally delivered lactation education program for expectant mothers of premature infants and their support person (SP) on timing of initiation of milk expression, lactation success, and stress

Specific aims are as follows:

Aim 1: To evaluate the feasibility of antenatal BM pumping education for SPs of mothers of preterm infants. Issues related to recruitment, randomization acceptance of the intervention, and refinement of the education materials and process will be scrutinized. Aim 2: To estimate variability of outcome measurements and effect sizes needed to calculate the sample size for a subsequent larger, adequately powered, randomized clinical trial

Research Plan:

Research Design

A randomized clinical trial will be conducted to determine the effect of a prenatally delivered lactation educational program for expectant mothers of premature infants and their SP on timing of initiation of milk expression and lactation success. Timing of lactogenesis stage II will be documented, volume of breast milk produced will be measured for the first 3 weeks following delivery and duration of lactation will be documented. Stress regarding the initial milk expression session will be measured. Breast milk sodium levels will be measured at Day 1-7, Day 14 and 21

Sample and Setting

80 mothers who have been hospitalized anticipating the delivery of a premature infant will be sampled by convenience from a maternity unit at Shands Teaching Hospital, a Level III tertiary care center. The hospital is part of the University of Florida and includes a Level III (52 bed) NICU. The hospital catchment area encompasses North Central Florida and Southern Georgia, a predominantly rural and semi-rural population. 120 VLBW infants per year are delivered with 95% of these women electing to express breast milk for their infants. This will also include enrollment of 80 support persons as a couplet with mom.

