Measurement of milk volumes by weight will occur at the initial expression session, for the first 7 days, and on day 14 and 21. (see Table 2 for a list of all instruments). If the infant breastfeeds during the 24-hour period, test weighing will be used to calculate breast milk consumed. *Test weighing* or the weighing of infants prior to and following breastfeeding, has been shown to be an accurate method of determining intake during breastfeeding in preterm infants. Prior to each breastfeeding session, infants will be weighed by the nurse assigned for patient care, and weight will include the clothing, diaper and/or blankets infant is wearing. Following completion of the breastfeeding session, the infant will be weighed again, clad in the same clothing as with initial weight. Infants will be weighed on the Baby Weigh scale (Medela, Inc, McHenry, III) to the nearest 0.2 g. The Baby Weigh scale is a portable electronic digital scale that is accurate to within 0.2 grams. The scale will be calibrated by the study coordinator prior to initiation of the study and after every 10 measurements, using 0.2mg, 1 mg, 10mg and 50 mg weights. All weights will meet or exceed ASTM (American National Standards Institute) specifications and will be calibrated by a NVLAP (National Institute of Standards and Technology) accredited lab. The difference between the pre and post-feeding weights will be recorded on the Breastfeeding Data Collection Form taped at the infant's bedside and will be added to the total amount the mother expressed during that 24-hour period (Appendix E).

A < 0.5 mL of breast milk will be obtained daily (if the mother is expressing > 5mL of breast milk per day) daily during days 1-7, day 14, day 21 and the sodium level analyzed

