Maternal mood can impact breastfeeding success in term infants and it is possible it may also impact BM production and timing of lactogenesis stage II in mothers of VLBW infants. Prior to her discharge from the hospital and 7 days following delivery, mothers will be asked to complete the MAACL-R; a standardized instrument with well-documented psychometric properties that assesses mood states by using positive and negative mood state scales for Anxiety, Depression, Hostility, Positive Affect and Sensation Seeking. It consists of 132 adjectives at or below an 8th grade reading level, takes approximately 3 minutes to complete. This test has been successfully used in lactating mothers of premature infants and was used in our previous

research. The second test will be completed around day 7 and will be provided to mothers prior to discharge. Mothers will be phoned by the research coordinator on to remind them to complete the test. Mothers will return the test when they visit their infant and results will be manually scored by the research coordinator.

Table 2. Instruments (Logs)

| Variable | Instrument | Measurement |
|---|---------------------------------------|--|
| Demographics (Appendix F, G) | Log maintained by Research Assistant | Age, parity, diabetes, pregnancy induced hypertension, mode of delivery, type of anesthesia, experience with breastfeeding, smoking, obesity, antenatal steroids |
| Lactation Factors (1-3 below) | | |
| 1. Onset of lactogenesis stage II | Log maintained by Research Assistant | Date and time of sensation of breast fullness Corresponding breast milk measurement |
| 2. Sodium level in breast milk | Log maintained by Research Assistant | Date/Sodium level in breast milk corresponding to onset of lactogenesis II |
| 2. Milk volume | Log maintained by Research Assistant | Daily total breast milk weight for days 1-7 24 hour sample at Day 14,21 |
| 3. Milk volume alternative for breastfed infants | Log maintained by Research Assistant | (Test weighing) - difference in infant's weight before and after feeding as indicator of breast milk intake. |
| Kangaroo care | Log maintained by RA | Incidence and length of kangaroo care in minutes extracted from medical record |
| Infant breast milk intake | | |
| 1. Weekly percentage of breast milk received by infant during first 3 weeks of life | Log maintained by Project Coordinator | Data extracted from medical record |

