| 2. Percentage of breast milk feedings at discharge | Log maintained by Project Coordinator | Data extracted from medical record |
| Post partum questionnaire | Log maintained by RA | Completed by RA or PI |
| Indicator of stress | Log maintained by RA | Completed by RA or PI |

Beginning 24 hours after delivery and continuing daily, mothers will be questioned (either in person or over the phone) regarding a sudden feeling of fullness in their breasts as an indicator of the onset of lactogenesis II. This has been a traditional method of determining the timing of lactogenesis stage II and has been shown to correlate with actual timing of this stage. (Appendix I) We will confirm the reliability of self-report by determining whether >100mL of milk is produced per a 24-hour period.

The percentage of breast milk the infant receives week 1, day 14, day 21 and the percentage of breast milk the infant is receiving upon discharge (mL/kg/d for the week prior to discharge) will be collected from the medical records. Neonatal nurses and physicians caring for the infants will not be told of the mother's assigned group (Appendix K.L).

Equipment

A simultaneous electric Symphony Plus Breast Pump ® (Medela, Inc.) will be used during hospitalization, and infant visitation and the same pump will be provided to all mothers enrolled in the study for home use while their infant is hospitalized. These are hospital-grade pumps that can be used for simultaneous breast milk expression (both breasts at the same time). Milk will be weighed on a Scout Balance electronic scale, a portable digital scale accurate to within 0.1 grams (Scout Balance, Florham Park, NJ). The scale contains an external calibration mechanism, stabilizes within three seconds, and will be calibrated by the research assistant prior to initiation of the study and after every 10 measurements using 0.1mg, 1mg, 10mg and 50 mg weights. All weights will meet or exceed American National Standards Institute (ASTM) specifications and will

be calibrated by a National Institute of Standards and Technology (NVLAP) accredited lab. The scale will be placed on the same platform at all times and will be wiped clean with a moist cloth and dried between each weighing.

Data Entry and Management

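### The check on self-reported lactogenesis II timing is a one-sided volume threshold: it cannot detect late reports and does not test timing

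*Combined protocol and SAP*

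**What the plan says.** The protocol treats the onset of lactogenesis stage II as an outcome in time. Research Design states: "Timing of lactogenesis stage II will be documented". Table 2 gives the onset entry as "Date and time of sensation of breast fullness Corresponding breast milk measurement", and a further row logs "Date/Sodium level in breast milk corresponding to onset of lactogenesis II".

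The text after Table 2 sets out the collection: "Beginning 24 hours after delivery and continuing daily, mothers will be questioned (either in person or over the phone) regarding a sudden feeling of fullness". It then gives the check on that report: "We will confirm the reliability of self-report by determining whether >100mL of milk is produced per a 24-hour period". The sentence does not say which 24-hour period is meant. It gives no comparison of dates, agreement window, statistic or failure criterion, and does not say what happens to an unconfirmed report. No cut-off or comparison rule is given for sodium.

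Two other places matter. The background on lactation describes stage II partly as "increases in milk volume to over 100ml/d", an event that can be dated. The volume schedule under Procedure reads: "Measurement of milk volumes by weight will occur at the initial expression session, for the first 7 days, and on day 14 and 21".

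**The concern.** The quantity of interest is when milk came in, but the check asks only whether volume is above a threshold. Exceeding 100 mL on the reported day shows that milk had come in by then. It does not show that it came in then. A mother who notices or reports fullness late can therefore be labelled confirmed.

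Aim 2 estimates outcome variability and effect sizes to size a later trial, and timing of lactogenesis II is one of the outcomes. If self-report is declared reliable by a check that cannot see lateness, the next trial inherits a measure whose timing error has not been examined. A pilot is the natural place to examine it.

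**Working it through.** The plan states no agreement, power or precision figure for this check, so there is nothing to reproduce. The check below follows the logic of the rule.

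**Inputs from the protocol.** The threshold is more than 100 mL per 24 hours. Fullness is asked about daily from 24 hours after delivery. Volumes are measured on days 1–7, 14 and 21. There are 80 mothers.

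**Assumptions not in the protocol.** Volume stays above 100 mL once it has crossed. The distribution of crossing days, and the fraction q of mothers who never cross by day 7, are also assumed.

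Let C be the first day above 100 mL and R the reported day.

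**Reading A, any 24-hour period in days 1–7.** A mother passes if she ever crosses. R does not enter the rule. The pass rate is 1 − q: 100%, 80% or 60% for q = 0, 20% or 40%, whether reports are accurate, early, late or random.

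**Reading B, the period corresponding to the report (Table 2).** With persistence, a mother passes if she crosses and R ≥ C.

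| Reports | q = 0 | q = 20% | q = 40% |
|---|---|---|---|
| Accurate | 100% | 80% | 60% |
| 1, 2 or 3 days late | 100% | 80% | 60% |
| 1 or 2 days early | 0% | 0% | 0% |

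Late reports pass exactly as often as accurate ones; early ones are rejected.

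**Uninformative reports under reading B.** If R is independent of C with the same distribution p₁…p₇ and every mother crosses on days 1–7, then P(pass) = P(R ≥ C) = (1 + Σpᵢ²)/2.

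- Uniform on days 1–7: Σpᵢ² = 1/7 = 0.143, so P = 1.143/2 = 57%.
- Discretised normal, mean day 3.5, SD 1: (1 + 0.283)/2 = 64%.
- SD 1.5: (1 + 0.197)/2 = 60%.
- SD 2: (1 + 0.166)/2 = 58%.

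If a fraction q never cross, these are multiplied by 1 − q. For example, 0.64 × 0.8 = 51% and 0.57 × 0.6 = 34%.

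A separate simulation took crossing on days 2–7 with the most common day 3, 4 or 5:

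| Uninformative reports | q = 0 | q = 20–40% |
|---|---|---|
| Uniform on days 2–7 | 51–79% | 30–63% |
| True days shuffled among mothers | 62–64% | 37–51% |

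**A two-sided check on the same assumptions (q = 0).** Requiring R within 1 day of C, reports 2 or 3 days late pass 0% of the time. Uniform uninformative reports still pass 46–48%, so a window needs a chance-corrected measure beside it.

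**Precision available.** With 64 of 80 mothers agreeing (80%), the exact 95% interval is about 70% to 88%. With 32 of 40, it is about 64% to 91%.

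**The case against.** The strongest reply is that the check does some work. On the Table 2 reading it rejects premature reports, and on either reading it rejects mothers who never exceed 100 mL on a measured day. That group may not be small, since the background says: "Delayed or impaired lactogenesis stage II has been found in up to 82% of women who deliver prematurely". This stands. A reader might infer that the check can never fail or that uninformative reports always pass at least half the time. The documents do not support either: the 50% floor needs every mother to cross by day 7.

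Persistence above 100 mL is not stated in the documents. Recorded volume depends on expression frequency and on vials being brought in from home, so a daily total could fall back. This also stands, and the result for late reports is conditional on it.

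Daily questioning makes a report several days late less likely, because it would take several missed or negative contacts. The protocol also says self-report correlates with actual timing. Both points bear on how often lateness occurs. Neither lets the check detect it, and a correlation is compatible with a constant lag.

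A reader might also infer that the rule creates a spurious treatment effect. It does not. A lag in one arm would bias the outcome whatever the check, and the protocol gives no size for such a lag.

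Finally, nothing in the plan makes confirmed status a condition for entering an analysis, and the dates and volumes for days 1–7 will exist anyway. That limits the harm and makes the repair cheap. It does not make the stated rule a test of timing. Appendix I, cited beside the sentence, is not in the public text, so its content cannot be judged.

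**Conclusion.** The point holds in a limited form. As written, the check is a one-sided volume threshold. On the any-period reading, the result is independent of the reported date. On the corresponding-period reading, it can reject early reports and mothers who never cross, but it cannot detect late ones while volume stays above 100 mL.

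The result for late reports follows from the rule plus persistence and needs no assumed distribution. The pass rates for uninformative reports do need one: about 57–64% if all mothers cross on days 1–7 and reports share the crossing-day distribution, and about 30–63% across the scenarios in which 20–40% never cross. They illustrate weak discrimination and are not predictions for this trial.

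The change should be made, but the weight is moderate: this is a pilot with feasibility as Aim 1, and the outcome matters here through Aim 2.

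**What to change.** Replace the confirmation sentence with a comparison of dates.

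- For each mother, compare the day of reported fullness with the first measured 24-hour period above 100 mL in days 1–7.
- Among mothers with both events, report the signed difference in days, with its mean and 95% limits of agreement.
- Report the proportion agreeing within a window stated in advance (for example, same day and within 1 day), with a chance-corrected measure such as weighted kappa.
- Give all of these overall and by group.
- In the proportions, count mothers with only one of the two events in days 1–7 as disagreements. They cannot enter the limits of agreement, so give their number beside them.
- List separately onsets reported on days 8–13 or 15–20, when no volume is scheduled.
- Describe the result as agreement between two markers of the same stage. Use the word reliability only if a numerical criterion is fixed before the data are seen.

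The cost is a few sentences and a short extra analysis. The dated fullness reports and the daily volumes for days 1–7 are already collected. The downside is that the reported agreement may look less favourable than a pass/fail confirmation.
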